Working memory (WM) and executive functions are skills developed to deal with complexities in life and are necessary for effective and adaptive behaviors. WM is the cognitive system that entails maintaining information in mind over a short time to complete an activity. WM is one of the most important components of information processing. A dysfunction of the WM system may lead to problems in developing cognitive functions, including mental arithmetic, reading, decision making and reasoning. WM is constituted by three main components: the central executive, the phonological loop, and the visuospatial sketch pad. Each component works to store and manipulate information in a temporary short-term memory system that is essential to human memory [42]. Executive functions include the control and organization of complex cognitive operations that allow a person to plan strategies, solve problems, and modify behaviors as a result of new information. The frontal lobes play a crucial role in WM and epilepsy has an impact on working memory functioning [43]. Visuospatial working memory (VSWM) involves encoding, maintenance, and retrieval of object identity, particularly spatial position [44-47]. VSWM is especially important in children during letter/number recognition, reading, writing, and math by facilitating recall of shapes and colors as well as their positions and movements. Determination of hemispheric memory lateralization plays an important role in the presurgical epilepsy evaluation, and very few studies have been conducted in children. The comparisons between adults and children revealed a greater activation in large regions of the frontal, parietal and temporal lobes, basal ganglia, and cerebellum in adults, while children showed greater activity in several occipital regions [48]. In adults, verbal memory has been predominantly lateralized over the left temporal lobe and visual-spatial memory over the right hemisphere [49-51]. But in children with epilepsy, a clear pattern of hemispheric lateralization of visuospatial memory has not been thoroughly investigated and established, and more investigations are needed to further assess WM in epilepsy.

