The symbols and grid plane will be white on a black background. The type font will be Arial with 80pp size. Each trial will begin with a central fixation cross-displayed for 300 ms, followed by encoding, maintenance, and retrieval phases. The symbols and grid will appear for 1 s (encoding phase), then a blank inter-stimulus interval (ISI) will display for 1.5 s (maintenance phase). Next, the symbols and grid will appear for 1 s (retrieval phase). The subject will be tasked with indicating whether the encoding stimulus matched the retrieval stimulus using two buttons; one for "congruent" and the other for "incongruent" response. Button type will be counterbalanced among subjects. The task will take around 16 minutes. The visual stimuli will be projected through an LCD projector onto a white screen located about 0.5 m in front of the subject and subtending 1.0-4.0 and 0.5 degrees of horizontal and vertical visual angle, respectively. A MEG compatible keyboard will be used to measure the subject's responses for "congruent" and "incongruent". The subject will practice the memory task before going to the MEG system using a computer from MEG laboratory. This practice phase will consist of a short version of the memory task with duration of approximately 4 minutes.

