## **Data Analysis**

### ***Preprocessing***

MEG data will be exported for further analysis from the acquisition computer to the signal processing research software, Brainstorm [66] (<https://neuroimage.usc.edu/brainstorm/>), which is an open-source application dedicated to the analysis of brain recordings. Next, data will band-pass filtered between 0.5Hz to 100Hz and a notch filter will be applied for power-line noise removal (60Hz, 2nd order IIR notch filter with zero-phase lag). We will perform visual inspection to mark bad channels and segments. Data will be preprocessed for eye-blink and electrocardiogram reduction using a signal-space projection (SSP) technique [67]. The corresponding triggers recorded during acquisition will be used to import MEG epochs in the time window ranging from -200s to +800s with respect to the trigger [68, 69]. Baseline correction will be applied on the 200s before the trigger. Next, we will average across epochs to obtain an ERF waveform per subject for the language and memory tasks. Resting state data will use for baseline source imaging.

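### The single epoch window, read as milliseconds, leaves the 1.5 s maintenance phase of the memory trial out of the analysis

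*Combined protocol and SAP*

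**What the plan says.** Preprocessing (under Data Analysis) gives one epoch rule, to "import MEG epochs in the time window ranging from -200s to +800s with respect to the trigger", and one baseline rule: "Baseline correction will be applied on the 200s before the trigger". It then states that "we will average across epochs to obtain an ERF waveform per subject for the language and memory tasks". No other epoch is described anywhere, and the memory event that serves as trigger is not named.

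Memory Task sets out the trial:
- a "central fixation cross-displayed for 300 ms"
- encoding: "The symbols and grid will appear for 1 s (encoding phase"
- maintenance: "then a blank inter-stimulus interval (ISI) will display for 1.5 s (maintenance phase"
- retrieval: "the symbols and grid will appear for 1 s (retrieval phase"

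Background and Rationale says that "WM is the cognitive system that entails maintaining information in mind over a short time to complete an activity". The same section lists maintenance, with encoding and retrieval, as a component of visuospatial working memory. Statistical Analysis takes hemispheric dominance for memory as the left-right difference in activation while the task is performed.

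**The concern.** The task has a dedicated maintenance phase, the longest of its three memory phases, and the protocol describes working memory in terms of holding information in mind. One short window is nevertheless applied to both tasks. It fits a single-word auditory response: Background and Rationale places the late auditory components at 150-700 ms. A memory trial that runs 3.5 s from encoding onset is a different matter.

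This is separate from the unit printed in the sentence and from the unnamed trigger. A sponsor who changed s to ms and named the encoding or the retrieval stimulus as trigger would still have no maintenance data in the analysis. At stake is what the memory index means. A left-right difference reported as memory dominance would carry no information from the phase in which the subject holds the pattern with nothing on the screen. The Statistical Analysis section says that the pilot will inform sample sizes for future research, so the gap could be passed on.

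**Working it through.** **Unit.** Taken literally, the epoch lasts 800 - (-200) = 1000 s. The memory task takes about 16 min = 960 s, and one trial as described takes 0.3 + 1 + 1.5 + 1 = 3.8 s. A 1000 s epoch with a 200 s baseline cannot be cut from such trials. Evoked components are given in milliseconds elsewhere in the protocol. The window is therefore read as -200 to +800 ms.

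**Trial timeline (Memory Task), with encoding onset at 0 ms.** Fixation -300 to 0; encoding 0 to 1000; maintenance 1000 to 2500; retrieval 2500 to 3500.

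**Formula.** For a trigger at time t, the baseline is [t - 200, t] and the analysed part is [t, t + 800]. The overlap of [a, b] with maintenance is max(0, min(b, 2500) - max(a, 1000)).

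| Trigger | t (ms) | Baseline | Analysed part | Maintenance in baseline | Maintenance analysed |
|---|---|---|---|---|---|
| Fixation onset | -300 | -500 to -300 | -300 to 500 | 0 ms | 0 of 1500 ms |
| Encoding onset | 0 | -200 to 0 | 0 to 800 | 0 ms | 0 of 1500 ms |
| Retrieval onset | 2500 | 2300 to 2500 | 2500 to 3300 | 200 ms | 0 of 1500 ms |
| Blank onset (not described) | 1000 | 800 to 1000 | 1000 to 1800 | 0 ms | 800 of 1500 ms |

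**Reading the table.**
- Encoding trigger: the window closes at 800 ms, 200 ms before maintenance begins.
- Retrieval trigger: the only maintenance data in the epoch are the last 200 ms, and 200/1500 = 13%. They form the zero reference, so any lateralised activity sustained through that interval is subtracted from the retrieval response.
- Blank-onset trigger: 800/1500 = 53% of maintenance is captured, with the last 200 ms of encoding as baseline. No section provides for this trigger. Background and Rationale describes evoked fields as following the onset of an external stimulus, and a blank screen does not obviously fit that.

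**Window that would cover the phase.** With an encoding trigger, maintenance enters only when the epoch runs past +1000 ms, and it is complete at +2500 ms. Retrieval ends at 1000 + 1500 + 1000 = +3500 ms. The phase durations are fixed, so one encoding trigger locates all three phases.

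**The case against.** The strongest reply is that the index is not empty without maintenance. Background and Rationale counts encoding and retrieval as parts of visuospatial working memory. It also ties late evoked components, which fall inside an 800 ms window, to association cortex and cognitive circuits. A retrieval-locked epoch spans the match judgement, which depends on what was held. All of this stands. A reader might infer that the index would come only from seeing a grid, or that Aim 2 is left unanswered for memory. The documents do not support either: the aim is to characterise memory circuitry, and no aim or analysis section promises a maintenance index.

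Three further replies can be made. The trigger is unspecified, so the zero coverage is conditional. That is true, but it holds for every stimulus onset in the trial, and the one exception is not described. The window is supported by cited sources that cannot be read here. Those sources might explain the choice, but they cannot change its overlap with this trial's timeline. Finally, this is a small feasibility pilot, and epochs can be imported again from stored recordings. That limits the harm and makes the correction cheap, but it does not put the maintenance phase into the plan as written.

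**Conclusion.** The point holds, limited to maintenance. Followed as written, the plan analyses 0 of the 1.5 s maintenance phase with a fixation, encoding or retrieval trigger. With a retrieval trigger it also uses the last 0.2 s (13%) as baseline. The memory dominance index would reflect encoding or retrieval responses but not maintenance.

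This rests on two assumptions: that milliseconds are meant, since seconds cannot be carried out, and that the trigger is one of the stimulus onsets in the described trial. If the sponsor intends a blank-onset trigger, coverage is 0.8 s (53%) and the plan should say so.

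Two further inferences are tempting but not supported. One is that the 0.5 Hz filter edge removes sustained maintenance activity; the band-pass order and roll-off are not given, so no size can be attached to this. The other is that maintenance must become the main memory index or be measured by source power. That is a preference, and source power would not fit the stated sequence of averaged evoked fields, sLORETA and the 3.2 nAm selection rule.

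**What to change.** Keep the -200 to +800 window, in ms, for language. For memory, in Preprocessing and Statistical Analysis:

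1. Correct the unit and name encoding onset as the trigger.
2. Import epochs from the pre-encoding baseline to +3.5 s.
3. Baseline on the pre-encoding interval, not on any part of maintenance. A 200 ms baseline fits inside the 300 ms fixation period, so no inter-trial interval has to be defined.
4. Report the left-right index separately for encoding (0-1.0 s), maintenance (1.0-2.5 s) and retrieval (2.5-3.5 s), as descriptive pilot results.

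The averaging and source-imaging steps can stay as they are. The same recordings serve, provided that encoding onset is marked in them; the protocol refers to recorded triggers without listing them, so the sponsor should confirm this. The cost is protocol wording, a little more analysis, somewhat more trials lost to artifacts because the epochs are longer, and three indices instead of one. Reporting the three descriptively avoids adding tests at the 0.05 level in a pilot of ten to fifteen subjects (Study Design and Procedures says ten, Study Population fifteen).

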## **Background and Rationale**

Pediatric epilepsy is the most common serious neurological disorder of childhood, affecting between 0.5-1% of children and young people under the age of 16 years [1]. Epilepsy is known to impair behavior, and adversely affect cognition and learning [2-4]. Antiepileptic drugs are effective medications available for epilepsy. However, many patients do not respond to this treatment and become resistant. Treatments such as the ketogenic diet, vagal nerve stimulators and resective and functional surgery have become available for these drug-resistant patients [5]. Surgery for removal of epileptogenic zone is the most effective treatment. The purpose of presurgical brain mapping is to facilitate surgical planning, prevent or reduce morbidity, and optimize the therapeutic effects of surgery. As part of the presurgical planning, assessment of hemispheric language and memory function is performed. The medical standard for determining the language dominant hemisphere and memory function prior to surgical resection is the intracarotid amobarbital test (IAT), also known as the Wada test [6]. It consists of an injection of sodium amobarbital into the left or right internal carotid arteries. This causes a temporary arrest of function in each hemisphere for approximately six to ten minutes, during which the unanaesthetised hemisphere is functionally assessed. A major drawback of this test is that it determines lateralization only, and does not allow intrahemispheric localization of language and memory functions. Moreover, because it is relatively invasive, this technique cannot be used with normal volunteers and is difficult to use with children. Additionally, the Wada test is associated with risks of stroke, infection, and hemorrhage [7]. Over the past decade, there is a significant discussion of the clinical utility of non-invasive brain imaging techniques (e.g. functional magnetic resonance imaging (fMRI)/ magnetoencephalography (MEG)) relative to the invasive Wada test for determination of hemispheric language and memory function. At present, while research has pointed to the better spatiotemporal resolution of both behavior and functional brain network organization available in brain imaging methods, the lack of language and memory tasks that map these functions in single individuals has reduced their clinical utility. The impact of epilepsy on language and memory are relevant not only from a clinical perspective but also because it sheds light on the underlying neurobiology of both processes. Identifying the patterns of language and memory organization prior to surgical intervention could therefore guide tailored resection and limit potential loss of function after surgery.

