fMRI is the most widely used of the minimally/non-invasive techniques for presurgical language mapping in children [11]. However, MEG is gaining increasing acceptance as a non-invasive method as an adjunctive part of the pre-surgical functional mapping procedure [12]. Especially for language identification in pediatric cases, the quiet environment of the MEG room and the head-motion-tracking methods available in recent MEG systems, increase the likelihood of success with language lateralization in young populations. Further, MEG allows examining both hemispheres simultaneously, which is especially useful in epileptic populations, in which language lateralization is more variable. MEG language localization studies have shown encouraging results with a wide variety of paradigms, especially in localization of receptive language areas that are well documented [13, 14] and validated [15, 16]. The suitability of MEG language lateralization protocols in adults as an alternative to the Wada procedure have been addressed with validation studies conducted using various methodologies and exhibit overall high concordance rates (about 86-92%) [17-20]. Language lateralization is calculated in both hemispheres by localizing dipole sources (equivalent current dipole, ECD model) accounting for late auditory evoked field (AEF) components (150-700 ms after stimulus onset). These late components localize to language-related areas (mainly within posterior temporal areas) of the brain regardless of the modality of stimulus presentation [21]. Depending on the activation task, the dipole sources can be used to identify the location of receptive (Wernicke's area) or expressive language-specific (Broca's area) cortex. The degree of hemispheric asymmetry in the duration or strength of activation can also be calculated as an index of hemispheric dominance for language functions. Estimations of language lateralization with MEG [22] have mainly been based on recognition memory tasks for spoken words [23] or by listening to synthesized vowel sounds [24]. Thus, most of the MEG language studies have focused on receptive language areas. However, other reports exist on frontal circuits in expressive language [25-27] and basal temporal areas during semantic language tasks (verb generation) [28, 29]. Recent MEG language studies have reported the feasibility of passive paradigms in children and adolescents under sedation [30] and during sleep [31]. A recent MEG study [32] uses a verbal memory and verbal fluency tasks showing activation of the left hippocampus and in Wernicke's area in favor of the left hemisphere. Authors found higher concordance rates between a verbal memory paradigm and language dominance in controls (using handedness as criterion) and in subjects with epilepsy (using fMRI or Wada as criterion), compared with a verbal fluency task. Only the concordance for verbal memory reached statistical significance, with 93% agreement. Previous studies in pediatric epilepsy have shown atypical language lateralization [33] and that the word recognition task is the only language comprehension task used in both children and adults that yields high concordance between MEG and the Wada test for language lateralization [22]. Despite all contributions of MEG in the assessment of language localization in typically developing individuals, studies in pediatric populations with epilepsy is still relatively small especially in single subjects, which is necessary for clinical utility.

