How epilepsy affects working memory performance is unclear but evidence suggest disruptions in the WM network [52]. MEG studies to examine the hemispheric lateralization of visuospatial memory circuitry prior to epilepsy surgery are severely lacking especially in children [53]. Importantly, visuospatial memory reorganization with seizure foci from the left and right hemispheres has not been investigated in detail. Although a significant role for the mesial temporal structure is suspected in visual-spatial memory, technological advances in MEG sufficient to detect hippocampal dynamics has become possible only recently [41]. Importantly, cortical stimulation and the Wada procedure cannot identify memory-specific circuitry or language circuit interactions whose activity patterns are developing in a non-typical brain environment due to on-going epileptic activity. Moreover, both cortical stimulation and the Wada are intimately related to the narrow time window and not suitable for delineation of neural pathways during complex tasks, and the repetition of these procedures to detect reliability cannot be performed.

Title: Pediatric Language and Memory Mapping in Refractory Epilepsy using Magnetoencephalography

PI: [name]

Site: Arkansas Children's Hospital

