## **Specific Aims**

### **Aim 1**

Feasibility of measuring language and memory functions in pediatric epilepsy with MEG brain signals.

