## **Tasks**

### **Receptive Language Task**

We will follow the standard protocols according to the American Clinical Magnetoencephalography Society (ACMEGS) [64]. The language task corresponds to an adapted version [30] of the continuous auditory word recognition protocol previously described by Papanicolaou [23] for determining hemispheric dominance of language function. The subject will perform a practice session where they will be instructed to "try to remember" a set of five audibly spoken English words, deemed targets. Target words are as follows: *jump, little, please, drink, and good*. Depending on the subject's overall verbal memory capacity, the target words will be presented once or twice during the practice phase. Subsequently, during the MEG recording, the five target words will repeat in a different random order, mixed with a different set of 40 distractors (non-repeating words) in each of three blocks of stimuli. Words will be presented for 1 s, one at a time, and randomly varied with an interstimulus interval between 2 s and 3 s. The auditory stimuli will be delivered binaurally through two long plastic tubes terminating in ear inserts at an intensity of 60 dB sound pressure level (SPL) at the subject's outer ear. Target words correspond to four monosyllabic and one disyllabic word with a mean frequency in the G6-7 corpus of 158 occurrences per million (range: 32-194 occurrences) [65]. For distractors, 40% of words will be disyllabic and the remaining will be monosyllabic with a mean frequency of occurrence of 150 words per million in the same corpus (range: 18-820). The subject's task will be to listen to the words and lift their index finger of the dominant hand whenever they hear a repeated target word (one of the five). After the language task, the subject will be given a break.

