### ***Statistical Analysis***

Overall: MEG and clinical parameters will be summarized as means, SD and ranges (for continuous and count data), as proportions (for binary and nominal data), or as proportions supplemented with mean scores (for Likert-scaled or other ordinal data). We will export the MEG

Title: Pediatric Language and Memory Mapping in Refractory Epilepsy using Magnetoencephalography

PI: [name]

Site: Arkansas Children's Hospital

source analysis parameters for further statistical analysis. This is a pilot study that will provide the preliminary sample size estimates to support future research.

**Hemispheric dominance:** Estimation of hemispheric dominance for language [69] and memory [68] will be calculated as the degree of activation of each hemisphere during performance of the task. We will derive an estimate of hemispheric dominance by calculating the difference in activation levels between the hemispheres.

**Group level:** For this pilot [research](#) study, we will perform a preliminary statistical analysis by comparing MEG source activations between hemispheres (left vs. right) with  $\alpha=0.05$  significance level using a research statistical software.

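### Each child's hemispheric dominance value is planned without a within-child error, and the only test, a group left-versus-right comparison, cannot supply one

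*Combined protocol and SAP*

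**What the plan says.** The Background and Rationale says of non-invasive imaging that "the lack of language and memory tasks that map these functions in single individuals has reduced their clinical utility". It describes paediatric epilepsy studies of language localisation as few, "especially in single subjects, which is necessary for clinical utility". Of the Wada test and cortical stimulation it says that "the repetition of these procedures to detect reliability cannot be performed".

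Aim 1 is "Feasibility of measuring language and memory functions in pediatric epilepsy with MEG brain signals", without a criterion for a successful measurement. Aim 2 is to characterise the circuitry in children with a left or right seizure focus.

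Each child has one MEG session (MEG Acquisition). In the language task, five target words are "mixed with a different set of 40 distractors (non-repeating words) in each of three blocks of stimuli". The Memory Task section plans 96 stimuli, 24 in each of four load-by-congruency conditions.

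Under Preprocessing, "we will average across epochs to obtain an ERF waveform per subject for the language and memory tasks". Source Imaging applies sLORETA to those averages and keeps source amplitudes of at least 3.2 nAm. Under Statistical Analysis, "We will derive an estimate of hemispheric dominance by calculating the difference in activation levels between the hemispheres". The only test is a group comparison of left and right activation at alpha 0.05. The same section says that the pilot will inform sample sizes for later research.

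**The concern.** The plan ends with one left-right difference per child and task, and nothing beside it shows how far that number would move with another set of trials. A large difference and one produced by trial-to-trial variation are reported in the same form.

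Three uses of the data are weakened:

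- **Aim 1.** Whether a child's value is reproducible within the session is useful evidence that something has been measured, and the plan does not report it.
- **Aim 2.** With 10 or 15 children, a few differences that are mostly noise could change the pattern described by side of seizure focus.
- **Later sample sizes.** A between-child SD from single values mixes true variation with measurement error, and the planned output cannot separate the two.

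**Working it through.** The documents give no power, precision or reliability figure, so there is none to reproduce.

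**1. Is within-child error estimated anywhere?** Three planned steps might seem to do so:

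- The empty-room covariance describes noise from the equipment and surroundings, not a child's trial-to-trial variability.
- The 3.2 nAm threshold selects sources.
- The resting-state recording supplies a baseline.

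None gives the sampling error of a dominance value.

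**2. Replication already recorded.**

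- Language: 3 × (5 + 40) = 135 words, assuming that each target occurs once per block.
- Memory: 4 × 24 = 96 stimuli, which agrees with the stated total.
- Bad segments will be removed, so these are upper limits.
- The memory count also needs confirming. The stated phases total 0.3 + 1 + 1.5 + 1 = 3.8 s, so 96 trials take 96 × 3.8 / 60 = 6.1 minutes, against a stated duration of about 16 minutes.

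**3. What an interval would show (assumed inputs).** Treat the index as a mean over n independent normal epochs with per-epoch SD s and true difference d. The SE is s/√n and the 95% half-width is 1.96 s/√n. P(wrong direction) = Φ(−(d/s)√n). P(interval excludes zero) = Φ((d/s)√n − 1.96) + Φ(−(d/s)√n − 1.96).

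| | 135 language epochs | 96 memory epochs |
|---|---|---|
| 95% half-width | 0.17 s | 0.20 s |
| Wrong direction, d/s = 0.05 | 28% | 31% |
| Wrong direction, d/s = 0.1 | 12% | 16% |
| Interval excludes zero, d/s = 0.1 | 21% | 17% |
| Interval excludes zero, d/s = 0.2 | 64% | 50% |
| Interval excludes zero, d/s = 0.3 | 94% | 84% |

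In 20,000 simulated children with d = 0, every difference had a direction, while an epoch-level test flagged about 5%.

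**4. Can the group test stand in?** In 20,000 simulated studies each child had a true difference of +1 or −1 with noise SD 0.2, so each was 5 SDs from zero. A paired t-test at two-sided 0.05 rejected as follows.

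| Share lateralised to one side | 10 children | 15 children |
|---|---|---|
| 50% | 6% | 5% |
| 70% | 24% | 34% |
| 90% | 82% | 95% |

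The test addresses the group mean. It can miss clear lateralisation in individuals when they differ in side, and the Background and Rationale itself says that language lateralisation is more variable in epilepsy.

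**5. Is agreement between the three language blocks enough?** Let z be the true difference divided by the SE of the full average. Each block has the right direction with probability p = Φ(z/√3), and all three agree with probability p³ + (1 − p)³.

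- z = 0: agreement 25%, full average in the wrong direction 50%.
- z = 1: agreement 39%, wrong direction 16%.
- z = 3: agreement 88%, wrong direction 0.1%.

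Agreement is only 0.393/0.25 = 1.6 times as likely at z = 1 as at z = 0, and 0.880/0.25 = 3.5 times at z = 3. It is a weak criterion on its own, so the interval should carry the decision.

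**6. Precision of a split-half correlation.** The 95% interval is tanh(atanh r ± 1.96/√(N − 3)). For an assumed r of 0.8 it is 0.34 to 0.95 with 10 children and 0.49 to 0.93 with 15. Both numbers of children appear (Study Design and Procedures; Study Population) and must be reconciled.

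**The case against.** The strongest reply is that this is a descriptive pilot and the plan makes no promise at the level of the child. Much of it stands.

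- **A reader might infer that the protocol contradicts itself.** It does not. Single-subject mapping appears as background on clinical utility, not as an aim. Study Design and Procedures describes feasibility in terms of recording both tasks. Risks and Benefits says the memory data will not be used for presurgical planning. The remark that Wada and cortical stimulation cannot be repeated does not commit this study to a reliability analysis.
- **A reader might infer that every child will be labelled left- or right-dominant, and that a known share of labels will be wrong.** The plan states a continuous difference and no cut-off or category. If the difference uses only sources above 3.2 nAm, a child with none in either hemisphere would have no direction at all. The wrong-direction percentages are therefore not error rates of a planned classification.
- **A reader might infer that averaging is the fault.** It is the ordinary way to obtain an evoked response, and the epochs remain available. The limitation lies in the planned output, not in the data.
- **The arithmetic is idealised.** The threshold makes the index non-linear, and the blocks may not be exchangeable, since the targets recur while the distractors change.
- **The dominance method is referred to cited sources** that cannot be checked here.

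None of this supplies a within-child error. The reply limits how strongly the point can be put, but the gap remains.

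**Conclusion.** The point holds as an inexpensive improvement. As written, the analysis gives each child a difference without an error, and its only test cannot show whether individual children are lateralised. Its size depends on quantities that the documents do not give. Under independent normal noise and an assumed true difference of 0.05 to 0.1 per-epoch SDs, the observed direction would be wrong in 12% to 28% of children for language and 16% to 31% for memory. With differences of 0.3 SDs, most children would have an interval that excludes zero. The group-test result rests on an assumed even split of sides and fades as one side predominates.

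A reader might go further and conclude that Aim 1 cannot be met or that Aim 2 cannot be interpreted. The documents do not support that: both aims can be addressed descriptively, but with less information than the recordings allow.

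**What to change.** Keep the full average as the point estimate, and add the following to the Statistical Analysis section:

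1. **Interval per child and task.** Resample epochs within each child, stratified by language block and by the four memory conditions. Re-average, re-run source imaging with the same threshold, recompute the left-right difference and report a 95% interval. Resampling the whole chain is preferable to the s/√n formula because of the threshold.
2. **Reliability.** Report agreement between language blocks, and between memory halves balanced across the four conditions, with a confidence interval, as a descriptive Aim 1 result. State that it is within-session reliability only, since there is one session, and that it is imprecise with 10 to 15 children.
3. **Wording of results.** Describe a child as left- or right-lateralised only if the interval excludes zero, and otherwise as indeterminate. Do not write that such a child is not lateralised, because an inconclusive interval is not evidence of symmetry.

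Confirm the number of memory trials beforehand. The cost is modest extra computation on data already to be recorded, noisier sub-averages, and some children reported as indeterminate. No extra scanning is needed.
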